8 SAFETY ANALYSES

8.1 Analyses of Primary Objectives of Safety

Safety analyses will be descriptive and based on the safety population, defined as all subjects who received a dose of trial treatment. Safety will be summarized overall and by individual treatment arms based on solicited short-term reactogenicity post-injection on Day 0 - 6, 28-day all AE profile by MedDRA preferred term, and 1-year MAE, SAE, and SNMC profiles post-injection on Day 0. All AEs, including MAEs, SAEs, and SNMCs will be tabulated by severity, related (possibly, probably, or definitely vs non-related per investigator assessment), and severe and related. The number and percentage (with 95% CI) of subjects in each treatment group with a given term will be summarized. A listing and narratives of SAEs will also be produced.

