that a slightly higher frequency of severe solicited AEs occurred among Quad-NIV recipients (3.2%) as compared with Fluzone HD recipients (1.3%) and to a lesser extent Flublok (2.6%); however, the 95% confidence intervals were overlapping among all groups. Severe fever was not reported in any treatment group.

Unsolicited AEs were reported by similar proportions of subjects who received 240 μ g Quad-NIV with 75 μ g Matrix-M1 (18%) and Fluzone HD (20%), and slightly less in the Flublok group (15%), through Day 28. Reports of severe unsolicited AEs were uncommon and reported in 2% of subjects in the Quad-NIV group and 1% of subjects in each of the active comparator groups. One severe event each of blood urea increased, anxiety, and nephrolithiasis was reported in the Quad-NIV group (3/156 subjects); acute sinusitis, dehydration, and hypokalemia in the Fluzone HD group (1/153 subjects); and hypertension in the Flublok group (1/151 subjects); none of these events were reported by the investigator as related to study treatment.

MAEs were reported in a similar proportion of subjects across all groups (7% Quad-NIV [240 μ g HA with 75 μ g Matrix-M1]; 9% Fluzone HD; 6% Flublok) with diagnoses spanning several SOCs, most commonly infections and infestations, representing common intercurrent illnesses with no apparent clustering by treatment group. SNMCs were reported in 2% of Quad-NIV subjects and 1% of Fluzone HD and Flublok subjects. Similar to MAEs, the diagnoses span several SOCs representing common intercurrent illnesses in this older adult population with no apparent clustering by treatment group.

No serious adverse events (SAEs) leading to death or considered related to study treatment have been reported to date. SAEs were reported in one subject each in the 240 μ g Quad-NIV with 75 μ g Matrix-M1 group (malignant melanoma) and the Fluzone HD (dehydration) group; no SAEs have been reported to date in the Flublok group. Generally, the rate of SAEs is consistent with the rate of 1.3% within 30 days post-vaccination reported in the Fluzone HD USPI (June 2018).

Overall, the safety and reactogenicity profiles of various formulations of Quad-NIV were generally comparable to both active comparator influenza vaccines based on available data through Day 28.

1.6.1.2 Immunogenicity Through Day 28

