1.8 Expected Risks from Vaccination with Quad-NIV With or Without Matrix-M1 Adjuvant

The expected risk of vaccination with Quad-NIV in combination with Matrix-M1 adjuvant can be directly extrapolated from available safety data through Day 28 from the previous Phase 2 trial (qNIV-E-201), which tested Quad-NIV alone or adjuvanted with Matrix-M1 in adults \geq 65 years of age (n = 1375 subjects) compared with Fluzone HD and Flublok Quadrivalent.

Nanoparticle Influenza	Vaccine, Quadrivalent	Confidential	qNIV-E-301 Protocol
Novavax, Inc.	Version 4	4.0 - 31 October 2019	Page 29

To date, there have been a total of 1068 human exposures to Quad-NIV with or without Matrix-M1 adjuvant.

Overall, the safety and reactogenicity profile of all Quad-NIV formulations/groups have been generally comparable to the active comparator influenza vaccines (Fluzone HD and Flublok Quadrivalent) based on available data reviewed through Day 28. A slightly higher frequency of severe solicited AEs occurred among subjects who received 240 µg Quad-NIV with 50 µg Matrix-M1 (3.3%) or 240 µg Quad-NIV with 75 µg Matrix-M1 (3.2%) relative to the active comparators (delta of < 1%); however, the 95% confidence intervals were overlapping among all groups. Injection site pain was the most common local AE (19%) followed by swelling (7%). In the group that received 240 µg Quad-NIV with 75 µg Matrix-M1, the most common systemic AEs (> 10%) were headache (15%) and muscle pain (10%). Reports of respiratory/facial AEs were generally infrequent and occurred in $\leq 5\%$ of subjects, with the exception of cough and sore throat, which occurred in 8% of subjects. Severe events occurring in subjects who received 240 µg Quad-NIV with 75 µg Matrix-M1 included nausea, fatigue, headache, sore throat, diarrhea, vomiting, chills, joint pain, muscle pain, difficulty swallowing, and eye redness, although these did not occur in significantly greater proportions than in subjects who received Fluzone HD or Flublok. Persistence of these signs and symptoms beyond 7 days after injection occurs uncommonly and is not expected. Occurrence of these solicited signs and symptoms with characteristics consistent with the definition of a SAE (ie, need for an urgent and significant medical intervention, and/or hospitalization, and/or residual disability) is also not expected.

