2.2 Study Endpoints

2.2.1 Primary Endpoints

• Comparative HAI antibody responses (assayed with egg-propagated virus) on Day 28, summarized in terms of the ratio of geometric mean titers (GMTs) AND seroconversion rate (SCR) difference, between subjects receiving Quad-NIV or Fluzone Quadrivalent for all 4 vaccine homologous influenza strains (ie, 2 influenza A and 2 influenza B strains).

Non-inferiority for each homologous strain will be demonstrated if:

○ The lower bound of the two-sided 95% CI on the ratio of the GMTs $(GMT_{OuadNIV}/GMT_{Fluzone})$ is ≥ 0.67 ,

AND

- The lower bound of the two-sided 95% CI on the difference between the SCRs ($SCR_{QuadNIV}$ - $SCR_{Fluzone}$) is \geq -10%.
- Number and percentage (95% CI) of subjects with solicited local and systemic adverse events over the 7 days post-injection (ie, Day 0 through Day 6, inclusive); all adverse events through 28 days post-injection (ie, Day 0 through Day 27, inclusive); and MAEs, SAEs, and SNMCs including AESIs through 1 year post-injection.

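### Safety is a primary objective, yet the plan reports only a percentage and 95% CI within each arm: no between-arm difference, and no upper limit on any excess of reactions

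*SAP*

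**What the plan says.** Protocol 2.1 and SAP 2.1.1 list describing the safety profile as a primary objective. The matching endpoint in SAP 2.2.1 is a within-arm quantity: "Number and percentage (95% CI) of subjects with solicited local and systemic adverse events over the 7 days post-injection", with corresponding summaries for all AEs over 28 days and for MAEs, SAEs and SNMCs, including AESIs, over one year. SAP 8.1 states that "Safety analyses will be descriptive and based on the safety population" and then: "The number and percentage (with 95% CI) of subjects in each treatment group with a given term will be summarized". Protocol 10.4.3 says the same. Nothing in SAP section 8 provides a risk difference, a ratio or any other between-arm interval, and the method for the within-arm safety CI is not named. For immunogenicity, SAP 7.1.1 and 7.2 do specify a Newcombe interval for the between-arm difference in seroconversion and seroprotection rates.

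The Phase 2 background is relevant in two places. Protocol 1.6.1.1 gives severe solicited AEs as 3.2% for the formulation taken forward, 1.3% for Fluzone High-Dose and 2.6% for Flublok, and adds: "however, the 95% confidence intervals were overlapping among all groups". Protocol 1.8 gives 3.3% and 3.2% for the 50 µg and 75 µg adjuvant groups, "relative to the active comparators (delta of < 1%); however, the 95% confidence intervals were overlapping among all groups".

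**The concern.** The question a licensure reader asks of a randomised safety comparison is how large an excess of reactions the data leave open. Two separate within-arm intervals do not answer it directly. They leave the reader to compare the arms by eye, and the usual way of doing so, checking whether the intervals overlap, is much stricter than an interval on the difference. The Phase 2 text used that reading for the one category where it noted more severe events with Quad-NIV. If the Phase 3 tables were read in the same way, a real excess could be described as comparable, with no bound attached.

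Separately, the expected-risk text in Protocol 1.8 gives a smaller Phase 2 difference than the protocol's own rates support for one of the two comparators.

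**Working it through.** **The plan's own safety figures.** SAP 9 states two for 1325 Quad-NIV recipients, and both reproduce. P(at least one event) at a true rate of 0.18% is 1 - (1 - 0.0018)^1325 = 90.8%. The one-sided 95% upper bound after zero events is 1 - 0.05^(1/1325) = 0.226%, which rounds to the stated 0.2%. Both concern one arm and say nothing about a difference.

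**The Phase 2 difference in Protocol 1.8.** From the rates in Protocol 1.6.1.1 and 1.8:

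| Quad-NIV group | minus Fluzone HD (1.3%) | minus Flublok (2.6%) |
|---|---|---|
| 75 µg (3.2%) | 1.9 points | 0.6 points |
| 50 µg (3.3%) | 2.0 points | 0.7 points |

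A difference under 1 point holds only against Flublok. Pooling the comparators does not recover it: with inferred counts of 2/153 and 4/151, the pooled rate is 6/304 = 2.0%, and 3.2 - 2.0 = 1.2 points. The denominators 156, 153 and 151 are those printed for unsolicited AEs in 1.6.1.1; the event counts are inferred from the percentages. With 5/156 against 2/153, the difference is 1.9 points, Newcombe 95% CI -1.9 to 6.1.

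**Why overlap is insensitive.** With within-arm standard errors s1 and s2, Wald intervals separate when the observed difference exceeds 1.96(s1 + s2). A Wald interval on the difference excludes zero when it exceeds 1.96√(s1² + s2²). At 3.2% and 1.3% with n = 1325:
- s1 = √(0.032 × 0.968/1325) = 0.00484 and s2 = √(0.013 × 0.987/1325) = 0.00311.
- Separation needs 1.96 × 0.00795 = 1.56 points; the difference interval needs 1.96 × 0.00575 = 1.13 points.
- With a true difference of 1.9 points, the chance of falling short is Φ(-(1.90 - 1.56)/0.575), about 28%, and Φ(-(1.90 - 1.13)/0.575), about 9%.

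**Exact check.** Sum the product of the two binomial probabilities over all pairs of counts. Count overlap unless the Quad-NIV lower limit exceeds the comparator upper limit. Count the excess as missed by Newcombe unless its lower limit exceeds zero. With 1325 per arm:

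| True rates | Overlap: Clopper-Pearson / Wilson / Wald | Missed by Newcombe difference CI |
|---|---|---|
| 3.2% vs 1.3% | 32.7% / 28.7% / 27.0% | 8.3% |
| 3.2% vs 2.6% | 97.6% / 97.0% / 96.7% | 85.5% |

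With 1195 per arm and 3.2% vs 1.3%, the overlap range is 33-39% and the Newcombe miss rate is 11.1%.

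**What the difference interval would report.** Take 42/1325 (3.2%) with 34/1325 (2.6%). The Wilson limits are 2.35-4.26% and 1.84-3.56%. The difference is 3.17 - 2.57 = 0.60 points. The Newcombe upper limit is 0.60 + √((4.26 - 3.17)² + (2.57 - 1.84)²) = 1.9 points and the lower limit is 0.60 - √((3.17 - 2.35)² + (3.56 - 2.57)²) = -0.7 points. The interval does not exclude zero, but it says the data are compatible with at most about 1.9 extra severe reactions per 100.

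**The case against.** The strongest reply is that the analysis matches its objective. The objective is to describe, the analysis is labelled descriptive, and the tables give counts by arm and severity, so any reader can compute the difference. That stands: nothing is wrongly calculated and no information is lost. It does not explain why the between-arm estimate should be left to the reader when the SAP already prespecifies that estimate for response rates.

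A reader might infer that this trial will judge safety by overlapping intervals and so miss an excess about a third of the time. The documents do not support that. Overlap appears only in the Phase 2 narrative, and no Phase 3 section adopts it. Nor did the Phase 2 conclusion of comparability rest on overlap alone: Protocol 1.6.1.1 also compares solicited and unsolicited AEs, MAEs, SNMCs and SAEs by percentage, and Protocol 1.8 says individual severe events were not significantly more frequent than with the comparators.

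A reader might also treat 1.3% as the rate to expect in the control arm. It belongs to Fluzone High-Dose. The comparator here is Fluzone Quadrivalent, and the documents give no severe solicited rate for it. Against the Flublok rate of 2.6%, the proposed interval would seldom detect the excess either.

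Finally, the Phase 2 difference is not an established signal: on the inferred counts its interval runs from -1.9 to 6.1 points.

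**Conclusion.** The point holds as an inexpensive improvement, not as an error in the analysis. For a primary safety objective, the plan gives no between-arm estimate and no upper limit on an excess.

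The possible gain depends on the comparator rate, which the documents do not supply. At 3.2% vs 1.3%, reading overlap would miss the excess in about 27-33% of trials, depending on the CI method, against about 8% for the difference interval. At 3.2% vs 2.6%, both would usually miss it (about 97% and 86%), and the benefit is only that an upper limit is stated. These figures assume independent binomial counts, 1325 evaluable subjects per arm, and a reader who relies on overlap; they are illustrations, not properties of the SAP.

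The inconsistency between Protocol 1.8 and 1.6.1.1 is real and needs no assumption, but it is confined to background text and affects no Phase 3 analysis.

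**What to change.** 1. In SAP 8.1, add the Quad-NIV minus Fluzone Quadrivalent risk difference with a two-sided 95% Newcombe CI, the method already given in SAP 7.1.1. Apply it to any and severe solicited local and systemic AEs, to any and severe unsolicited AEs through the 28-day window, and to MAEs, SAEs, SNMCs and AESIs through one year. Label the intervals descriptive and unadjusted, without p-values. State that any claim of comparability will rest on this interval and its upper limit, not on overlap of the arm CIs.
2. Minor: reconcile Protocol 1.8 with 1.6.1.1 by giving the difference against each comparator separately (1.9-2.0 points against Fluzone High-Dose, 0.6-0.7 points against Flublok).

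The cost is a few table columns and short wording changes; design, sample size and error control are untouched. The one downside is that, with several unadjusted intervals, some will exclude zero by chance, which is why the descriptive label matters.

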recommended for inclusion in the 2019-2020 Northern hemisphere seasonal influenza vaccine [VRBPAC 2019, WHO 2019], co-formulated with 75 µg Matrix-M1 adjuvant, as compared to a US-licensed quadrivalent seasonal influenza vaccine comparator, Fluzone Quadrivalent, to generate data to support licensure of Quad-NIV for the prevention of influenza disease in adults > 65 years of age.

1.1 **Study Design**

This is a Phase 3, randomized, observer-blinded, active-controlled trial to evaluate the immunogenicity and safety of 240 µg Quad-NIV co-formulated with 75 µg Matrix-M1 adjuvant against a licensed comparator in clinically stable adults \geq 65 years of age to be conducted in the United States. Approximately 2650 eligible subjects will be enrolled and randomized at a 1:1 ratio into 1 of 2 treatment groups, as shown in Table 1 below. The active group (Group A) and the comparator group (Group B) will each consist of approximately 1325 subjects. Both groups will be stratified by site, age (65 to < 75 and \ge 75 years), and history of prior year receipt of the 2018-19 influenza vaccine. On Day 0, all subjects will receive a study treatment as indicated in Table 1 by intramuscular (IM) injection. Total injection volumes for Quad-NIV will be 0.5 mL. Trial follow-up for each subject will span approximately 1 year from the Day 0 injection. It is anticipated that a percentage of the randomized trial subjects will not complete the trial. Subjects who withdraw or are discontinued will not be replaced.

Table 1: Trial Design for qNIV-E-301

		Day 0 Trial Treatm	ent Injection			
Treatment Group	Vaccine	HA Dose per Strain, μg (H1N1/H3N2/By/By)	Matrix-M1 Adjuvant Dose	Injection Volume	Treatment Arm	Subjects Per Group
A	Quad-NIV	60, 60, 60, 60	75 μg	0.5 mL	Non-dominant	1325
В		2019-20 Fluzone Qu	ıadrivalent ^[1]		Non-dominant	1325
Total Trial Subjects				2650		

Abbreviations: B_V = B Victoria lineage; B_Y = B Yamagata lineage; HA = Hemagglutinin

Note: All subjects will receive a single vaccination by IM injection on Day 0. If the non-dominant arm is not available for injection, then the dominant arm will be used.

1.2 **Randomization and Treatment Assignments**

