8.2 Medically-Attended Events and Significant New Medical Conditions

These classes of events will be collected at all study visits, and if offered spontaneously by the subject at any time.

Medically-attended events (MAEs) are adverse events which result in an unscheduled visit to a healthcare provider due to symptomatic illness or injury. These may include office visits, clinic visits, home consultations, or emergency room evaluations for non-life-threatening events that do not result in hospitalization (life-threatening events or hospitalizations are SAEs, see Section 8.3).

Significant new medical conditions (SNMCs) are adverse events that are new (that is, not present at baseline), clinically significant (meaning that they imply an important change in the subject's long-term health status), and typically chronic (requiring an ongoing change in the subject's medical management). This category is not meant to include minor or transient diagnoses or age-related changes.

The eCRF will provide a field in which the investigator may designate AEs as MAEs, SNMCs, or both. Because of the significance of the designation for the subject's health, long-term medical management, and for evaluation of vaccine safety, SNMCs are expected to be substantiated diagnoses, not isolated symptoms which might or might not be a SNMC, and the investigator should record sufficient data in the eCRF to support the diagnosis.

Full details of MAEs and SNMCs (ie, nature, date of onset, and recovery (if applicable) as well as an assessment of severity, relationship to trial agent, seriousness, treatment, and outcome)

will be recorded in the source documentation and captured in the eCRF, and will require the investigator(s) causality assessment.

MAEs and SNMCs will be recorded and summarized from Day 0 to Day 28 for the unblinded data review and from Day 0 to Day 364 following study completion for the final analysis, for all subjects in the Safety Population. Note that MAEs and SNMCs are also included in the overall summary of AEs.

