9 SAMPLE SIZE CONSIDERATIONS

This study has a single comparison between Quad-NIV and Fluzone Quadrivalent at Day 28 post-vaccination for the primary immunogenicity objective. No adjustment of the Type I error rate for multiple comparisons is warranted since the simultaneous successes of all 8 comparisons planned for the 4 strains contained in the vaccines and the two endpoints (GMT and SCR) are required for the demonstration of the primary non-inferiority objective of the study.

Non-inferiority is defined as the lower bound of the 2-sided 95% CI on the ratio of GMTs (Quad-NIV vs Fluzone) ≥ 0.67 (ie, unadjusted 1-sided p-value < 0.025 against the null hypothesis of H0: Ratio of GMT < 0.67) and the lower bound of the two-sided 95% CI on the

difference of the SCRs (Quad-NIV - Fluzone) \geq -10% (ie, unadjusted 1-sided p-value < 0.025 against the null hypothesis of H0: Difference of SCRs < -10%).

For the calculation of sample size estimation, we used assumptions of true differences, ie, the ratio of GMTs (Quad-NIV vs Fluzone Quadrivalent) is 1.0 for all 4 homologous strains, and the difference of the SCRs is -2% for each of the 4 homologous strains, based on the average performance in the previous trial (qNIV-E-201). To achieve an overall 90% power (ie, ~ 97.5% power for each of the 4 strains) to demonstrate a non-inferiority margin for SCR difference of -10%, the SCR of reference group (Fluzone Quadrivalent) is assumed to be 0.5 and the SCR of treatment group (Quad-NIV) is assumed to be 0.48 under the null hypothesis of inferiority (H0: Difference of SCRs < -10%). The significance level of the testing is 0.025. Sample size was estimated to be 1195 in each group by assuming equal size in each group. The sample size accounted for a 10% attrition rate for the per-protocol population such that the primary analysis population for all immunogenicity endpoints will be 1325 in each group.

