12.5 Missing, Unused, and Spurious Data

In general, there will be no substitutions made to accommodate missing data points. All data recorded on the eCRF will be included in data listings that will accompany the CSR.

When tabulating AE, Concomitant Medications, and Hospitalizations data, partial dates of event onset will be handled as follows:

- If the day of the month is missing, the onset date will be assumed to be the date of the Day 0 vaccination or first of the month, whichever is later, in order to conservatively report the event as vaccine-emergent.
- If the month or year (or both) of the onset date is missing, impute month or year (or both) which makes the imputed date most adjacent to the first dosing date.
- If the onset day and month are both missing, the event onset will be coded to the date of the Day 0 vaccination or 1st January of the year, whichever is later, in order to conservatively report the event as vaccine-emergent.
- A completely missing onset date will be coded as the date of the Day 0 vaccination, unless the end date suggests it could have started prior to this in which case impute the 1st January of the same year as the end date.
- When imputing a start date ensure that the new imputed date is prior to the end date of the AE or med.

A conservative approach will be taken to assess the relationship of an event to test article: if the relationship of an event is missing, it will be considered treatment-related. Missing severity for an AE will not be imputed.

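### The 1-year MAE, SNMC and SAE percentages are taken over everyone dosed, so subjects lost event-free before Day 364 count as full-year non-events and 1-year risk is modestly understated

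*SAP*

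**What the plan says.** - **Endpoint.** SAP 2.2.1 makes safety a primary endpoint, beginning with "Number and percentage (95% CI) of subjects with solicited local and systemic adverse events over the 7 days post-injection". The same bullet extends to MAEs, SAEs and SNMCs through one year.
- **Population and measure.** SAP 8.1: "Safety analyses will be descriptive and based on the safety population, defined as all subjects who received a dose of trial treatment". The summaries include "1-year MAE, SAE, and SNMC profiles post-injection on Day 0", and the statistic is "The number and percentage (with 95% CI) of subjects in each treatment group with a given term will be summarized". SAP 8.2 repeats the scope for MAEs and SNMCs: "from Day 0 to Day 364 following study completion for the final analysis, for all subjects in the Safety Population".
- **Incomplete follow-up.** SAP 1.1: "It is anticipated that a percentage of the randomized trial subjects will not complete the trial". Leavers are not replaced.
- **Missing data.** SAP 12.5: "In general, there will be no substitutions made to accommodate missing data points". The rules that follow deal with partial onset dates, missing relationship and missing severity. SAP 12.4 on withdrawals is operational and gives no analysis rule.
- **Attrition.** The only figure is in SAP 9: "The sample size accounted for a 10% attrition rate for the per-protocol population".
- **Mitigating provisions.** Protocol 6.5 asks sites to make reasonable efforts to query early leavers for MAEs, SNMCs and SAEs. SAP 4 tabulates discontinuations before Day 364 by arm and reason, and lists day of last contact. SAP 8.3 counts death as an SAE outcome.

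**The concern.** The denominator assumes that all dosed subjects were watched for a year, whereas the numerator can contain only events that were seen. A subject last reached at Day 90 with no event adds one to the denominator and nothing to the numerator, exactly like a subject followed event-free to Day 364. The percentage therefore estimates the proportion with an event observed before loss, which is lower than the proportion with an event within a year. The confidence interval is centred on that lower quantity.

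Describing the 1-year safety profile is a primary objective, so a reader will take these percentages as 1-year risks. If loss were unequal between arms, the shortfall would be unequal too, and part of any difference between arms would reflect follow-up rather than vaccine.

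**Working it through.** **The plan's own safety figures (SAP 9).** With n = 1325 and a true rate of 0.18%, P(at least one event) = 1 − (1 − 0.0018)^1325 = 90.8% (stated as above 90%). With zero events, the one-sided 95% bound is 1 − 0.05^(1/1325) = 0.226% (stated as 0.2%). Both reproduce, and both treat all 1325 subjects as fully observed. As an outer limit, if 10% contributed no follow-up at all (n = 1192), they become 88.3% and 0.251%.

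**Shortfall of the crude percentage.** Assumptions:
- n = 1325 per arm (SAP 1.1).
- Constant event hazard λ, with 1-year risk r = 1 − e^(−λ).
- A fraction d lost, uniformly over the year and independently of events.
- r of 5%, 20% and 40%, and d of 5% and 10%. These values are assumed because the documents give neither quantity.

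Formulas:
- Chance that a leaver's event is seen before exit: s = 1 − (1 − e^(−λ))/λ = 1 − r/λ.
- Shortfall: b = d × (r − s).
- SE = √(r(1 − r)/1325).
- Coverage of r by a nominal 95% interval: Φ(1.96 − b/SE) − Φ(−1.96 − b/SE).

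For example, at r = 20%, λ = −ln(0.80) = 0.2231 and s = 1 − 0.20/0.2231 = 0.1037. Then r − s = 0.0963, so b = 0.48 points at 5% loss and 0.96 at 10%. SE = √(0.20 × 0.80/1325) = 1.10 points.

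| True risk r | s | SE (points) | Shortfall, 5% loss | Shortfall, 10% loss | Coverage, 5% loss | Coverage, 10% loss |
|---|---|---|---|---|---|---|
| 5% | 2.5% | 0.60 | 0.12 | 0.25 | 94.5% | 93.0% |
| 20% | 10.4% | 1.10 | 0.48 | 0.96 | 92.8% | 85.8% |
| 40% | 21.7% | 1.35 | 0.92 | 1.83 | 89.6% | 72.5% |

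The shortfall relative to r is 2.3–2.5% at 5% loss and 4.6–5.0% at 10% loss, that is, about half of d.

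**Check with another dropout shape.** With a constant dropout hazard δ = −ln(1 − d), the expected crude percentage is λ/(λ + δ) × (1 − e^(−(λ + δ))). At 10% loss, true risks of 5%, 20% and 40% show as 4.75%, 19.0% and 38.1%, which is nearly the same.

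**Unequal loss.** With equal true risk of 20% and loss of 5% in one arm and 10% in the other, the spurious difference is 0.96 − 0.48 ≈ 0.5 points, against an SE for the difference of √2 × 1.10 ≈ 1.55 points.

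**The case against.** **The plan delivers the endpoint it defines.** The endpoint is a number and percentage of subjects. The denominator is stated and missing data are not substituted, so the scoring of leavers is determined. This is correct: the plan is not silent or self-contradictory. What stands is that the resulting number is not the 1-year risk that its label suggests.

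**Existing provisions help.** Events up to exit are sought under Protocol 6.5, so leavers are not wholly unobserved, and SAP 4 shows how much follow-up was lost in each arm. The working already credits events seen before exit. Tabulating losses discloses the problem but does not correct the percentage or its interval, and an exit query cannot reach a subject who is lost.

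**Nothing is decided on these numbers.** Safety is descriptive, with no test or margin, and equal loss affects both arms alike. This limits the importance to presentation and interpretation.

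Stronger readings that a reader might infer, and why the documents do not support them:

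- *Subjects who die are scored as event-free.* Death is itself an SAE. For MAEs and SNMCs it is a competing event: a subject who has died has no later unseen event, so keeping that subject in the denominator does not bias the proportion low.
- *The intervals are badly wrong.* Extending the Phase 2 Day 28 MAE rate of 7% (Protocol 1.6.1.1) at constant hazard over 13 periods gives λ = 0.943 and a 1-year risk of 61.1%. At 10% loss the shortfall is then 2.6 points and coverage about 52%. That result needs both extremes: at 5% loss coverage is about 84%. If 7% is 11 of 156, its exact interval of 3.6–12.3% puts the 1-year risk anywhere from 38% to 82%. The same extrapolation for SAEs (1 of 156) gives coverage of 92–94% at 10% and 5% loss.
- *The plan expects 10% loss by Day 364.* The 10% is attrition from the per-protocol set, which depends on Day 0 and Day 28 serology and major deviations.
- *The arm with more dropout will look safer.* This is possible in principle, but neither document suggests that loss will differ by arm in this single-dose, observer-blinded trial.

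**Conclusion.** The point holds as a modest weakness in how the 1-year results are summarised. The crude Day 0–364 percentages understate 1-year risk by about half the loss fraction in relative terms. Over the assumed 5% to 10% loss that is negligible to small for SAEs and individual preferred terms. It can reach 1 to 2 points, with visible undercoverage, for a common class such as any-MAE.

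The size rests on assumed loss and event rates, a roughly constant hazard and loss independent of events. If subjects leave because of impending events the shortfall would be larger, and if healthier subjects leave it would be smaller. It does not affect the immunogenicity objective or any decision rule. It is a cheap improvement, not a flaw that threatens the trial's conclusions.

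**What to change.** In SAP 8.1–8.3, for the any-MAE, any-SNMC and any-SAE rows of the Day 0–364 tables only:

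1. Add the cumulative incidence of first event at Day 364, by arm, with a 95% CI.
2. Censor at the last safety contact, including any early-termination query. SAP 4 already derives day of last study contact from the discontinuation date. Where that date is later than the last contact actually made, use the contact.
3. Treat death as a competing event for MAE and SNMC. For SAE, death is an event.
4. Keep the crude percentages, labelled as *observed during follow-up*.

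A rate per 100 person-years would be a weaker choice, because it does not itself estimate 1-year risk and it leans on a constant hazard.

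The cost is SAP wording and one extra column, from onset and contact dates already collected. No visit, sample size or procedure changes. The downside is that the new column assumes loss is independent of events, which should be stated in a footnote beside the SAP 4 discontinuation counts by arm.
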